1.1.2. Second Single Dose, Cohorts 2A, 2B, 3A, and 3B

Table 2: Schedule of Events: Second Single Dose, Cohorts 2A, 2B, 3A, and 3B

Day (Window)	Clinical Research Unit (CRU) Inpatient Stay										Outpatient CRU Visits ^a			
	-1 (±10)	1	2	3-6	7	9	11	14	21	30	OV1 (±3)	OV2 (±5)	OV3 (±7)	OV4 ^b (±14)
Inclusion/Exclusion criteria ^c	X	X												
Complete physical with vital signs (BP, RR, HR, oral temperature, height, weight, BMI)	X													
Targeted physical with vital signs (BP, RR, HR, oral temperature)		X ^d	X	X	X			X	X	X	X	X	X	X
Safety ECG ^e	X	X			X					X				X
Laboratory evaluations (CBC with/platelets, serum chemistry, urinalysis)	X		X	X ^f	X			X	X	X	X	X	X	X
Virology screening (HBV, HCV, HIV)	X													
Virology screening (SARS-CoV-2)	X													
Urine Pregnancy ^g	X													
Drug/alcohol screen ^h	X													
Dosing of Study Drug (Cohorts 2 and 3 only)		X												
Reactogenicity/injection site inspection ⁱ		X	X	X										
PK sample collection ^j		X	X	X	X	X	X	X	X	X	X	X	X	X
Samples for metabolite identification ^k		X	X					X		X				X
Exploratory biomarker samples		predose		X ^f										
Anti-drug antibodies		predose						X		X	X	X	X	X
Nasopharyngeal swab/nasal wash collection ^l		predose	X	X	X	X	X	X	X	X				
Assess and record AEs ^m	X	X	X	X	X	X	X	X	X	X	X	X	X	X
Concomitant medications/procedures review ⁿ	X	X	X	X	X	X	X	X	X	X	X	X	X	X

Abbreviations: AEs = adverse events; BMI = body mass index; BP = blood pressure, CBC = complete blood count; COVID-19 = coronavirus disease 2019; CRU = clinical research unit; ECG = electrocardiogram; HBV = hepatitis B virus; HCV = hepatitis C virus; HIV = human immunodeficiency virus; HR = heart rate; hr = hour; ICF = informed consent form; PK = pharmacokinetic; RR = respiration rate; SARS-CoV-2 = severe acute respiratory syndrome coronavirus 2.

Schedule of Events: Second Single Dose, Cohorts 2A, 2B, 3A, and 3B

- a. For subjects in Cohorts 2A, 2B, 3A, and 3B: outpatient visits will occur at Day 45 (OV1), Day 84 (OV2), Day 126 (OV3), and Day 168 (OV4).
- b. For subjects who discontinue study early, the Day 168 procedures should be performed.
- c. Reconfirmation of inclusion and exclusion criteria (retesting of FSH not required) is to be completed at CRU check-in on Day -1 and prior to the second single dose of CD388 Injection or placebo on Day 1.

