3 STUDY DESIGN

3.1 General Description

This is a first-in-human (FIH), Phase 1, single-center, prospective, randomized, double-blind study of ascending single doses of CD388 Injection administered IM or SQ to healthy adult subjects followed by another single dose of CD388 Injection administered by the same route 3 months or 5 effective half-lives, whichever is longer, after the first dose in the middle and high dose groups (dosing may be adjusted for tolerability). The goals are to assess safety, tolerability, immunogenicity (anti-drug antibodies [ADA]), and PK of CD388.

Dose levels of CD388 to be assessed will follow an ascending single dose design with the starting dose based on findings from 3-month rat and monkey toxicology studies. Within each route (IM and SQ dose, route assignment is unblinded), subjects will be randomized to receive a single dose of CD388 Injection or saline placebo (treatment assignment is blinded) according to the design. It should be noted that each cohort will be divided into 2 groups identified as “sentinel” groups (randomized 1:1) and “main” groups (randomized 7:2):

- Low dose level: Cohort 1A (IM) and Cohort 1B (SQ) – each route n = 2 sentinel and n = 9 main
- Mid dose level: Cohort 2A (IM) and Cohort 2B (SQ) – each route n = 2 sentinel and n = 9 main
- High dose level: Cohort 3A (IM) and Cohort 3B (SQ) – each route n = 2 sentinel and n = 9 main
- Highest dose level: Cohort 4B (SQ) – n = 2 sentinel and n = 9 main

For each route, the sentinel or first group of 2 subjects (1 CD388: 1 placebo) at a dose level will be administered blinded study drug and closely monitored for safety for at least 1 week. If no drug-related SAEs or drug-related Grade ≥ 3 AEs have occurred, the subjects in the corresponding main group may be dosed within 24 hours. The observation duration may be adjusted for the sentinel groups in Cohorts 2A, 2B, 3A, 3B, and 4B based on data from previous cohorts.

Subjects in Cohort 4B will receive a single dose of CD388 or placebo. Subjects in Cohorts 2A and 2B and Cohorts 3A and 3B will receive a second single dose of CD388 Injection or placebo after washout of 3 months or 5 effective half-lives, whichever is longer, after the first dose if it is determined that the safety and tolerability of the first dose is acceptable upon review of the cumulative safety data.

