8 SAFETY ANALYSIS

Unless otherwise specified, all available data will be listed and summary tables for safety assessments will be presented by injection route (IM or SQ), CD388 dose, and pooled placebo for the safety population as detailed in [Table 6](#).

Continuous variables will be summarized (absolute values and change from baseline) using descriptive statistics. The TEAEs occurring after the first single dose and after the second single dose will be analyzed separately.

Table 6: Data Presentations for Safety Assessment

Data	Variables	Presentation
Adverse events	Adverse event, description, date and time, severity, relationship to study drug, action taken with study drug, whether the AE caused the subject to discontinue from the study, study days, and outcome, Duration of AE, Date and time of onset, date, and time of resolution.	
Listings:
 
• Reported AEs,• Serious Adverse Event (SAE) 
Summary Tables, including number and percentage of subjects experiencing:
 
• Treatment-emergent adverse events (TEAEs),• TEAEs related to study drug• TEAEs by severity,• Serious TEAEs,• Influenza-like TEAEs (reported during the outpatient follow-up period),• Adverse Events of Special Interest (AESIs),• TEAEs leading to study withdrawal• TEAEs leading to study drug withdrawal (cohorts 2a, 2b, 3a, 3b)• Overall summary will include:
○ At Least One TEAE○ At Least One Drug-Related TEAE○ Maximum Severity:
➢ Mild,➢ Moderate➢ Severe➢ Life-threatening➢ Death○ At Least One SAE○ At Least One Drug-Related SAE○ Death○ AE leading to study drug withdrawal (Pooling placebo from cohorts 2a, 2b, 3a, 3b)○ AE leading to study withdrawal
Concomitant medications	All medications taken during the study (as defined in the protocol and including prior medications that are continued), dose, units, route, indication/ reason taken, and date and time.	
Listing
 
• Note: includes coded terms (anatomic therapeutic chemical [ATC] level 4 and preferred name)

Data	Variables	Presentation																
Extent of exposure	Study drug administration dose, Route, units, date, time, Cohort	
Listing
																

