		
 • Table 10, Table 11, Table 12) by category. • Number and percentage of subjects with a laboratory value that is deemed PCS, for each scheduled post baseline assessment time point 	
Vital signs	Blood pressure, pulse, respiration rate, and body temperature	Listings: 
 • All vital signs values, • PCS vital sign values Summary Tables: 
 • Vital signs values and change from baseline by visit and timepoint. • Number and percentage of subjects with at least one post baseline PCS value will be summarized for the worst post baseline value. • Number and percentage of subjects with a vital sign value that is PCS, for each scheduled postbaseline assessment time point 	
Physical examination	Physical examination findings	Listing: 
 • All physical examination findings 	
12-Lead Digital Electrocardiograms	ECG interpretations and findings;	Listings: 
 • All ECGs, • Clinically significant ECGs, Summary Tables 
 • ECGs parameters values and change from baseline by visit and timepoint. • Categorical QT/QTc analysis by Visit and timepoint. 	
Reactogenicity/Injection Site Inspection	Reactogenicity/Injection Site Inspection findings	Listing Table	

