			x/xx (xx..x)		x/xx (xx..x)		x/xx (xx..x)		x/xx (xx..x)		x/xx (xx..x)		x/xx (xx..x)		x/xx (xx..x)		x/xx (xx..x)		x/xx (xx..x)		x/xx (xx..x)		x/xx (xx..x)			
			x/xx (xx..x)		x/xx (xx..x)		x/xx (xx..x)		x/xx (xx..x)		x/xx (xx..x)		x/xx (xx..x)		x/xx (xx..x)		x/xx (xx..x)		x/xx (xx..x)		x/xx (xx..x)		x/xx (xx..x)			
	Alanine aminotransfer ase (F)		x/xx (xx..x)		x/xx (xx..x)		x/xx (xx..x)		x/xx (xx..x)		x/xx (xx..x)		x/xx (xx..x)		x/xx (xx..x)		x/xx (xx..x)		x/xx (xx..x)		x/xx (xx..x)		x/xx (xx..x)			
	Alanine aminotransfer ase (M)		x/xx (xx..x)		x/xx (xx..x)		x/xx (xx..x)		x/xx (xx..x)		x/xx (xx..x)		x/xx (xx..x)		x/xx (xx..x)		x/xx (xx..x)		x/xx (xx..x)		x/xx (xx..x)		x/xx (xx..x)			

Date: VERSION - YYYY-MM-DD

Data Source: xxx

Program Source: xxx.sas

IM = Intramuscular; SQ = Subcutaneous

Note: n is the number of subjects who met the PCS criteria. Denominator (m) is the number of subjects with non-PCS baseline and at least one post-baseline assessment when calculating the percentage.

<Laboratory Panel> = Hematology; Chemistry; Urinalysis; Coagulation; Lipid;
<Programming Note>

ETC.= for SQ: Cohort 4B CD388 - Pooled Placebo
It can be presented separately (i.e., IM one page and SQ another).

Table 14.2.21 Teplate T5.1: Summary of Vital Signs (Safety Population)

Table 14.3.3.1
Summary of Vital Signs
(Safety Population)
<Parameter (Unit)>

Date: VERSION - YYYY-MM-DD Data Source: xxxx

Program Source: xxx.sas

IM = Intramuscular; SO = Subcutaneous; SD = Standard Deviation.

Note: Baseline is the measurement of the last predose measurement was used.

<Parameter (unit)> = Systolic Blood Pressure (mmHg), Diastolic Blood Pressure (mmHg), Pulse Rate (beats/min), Temperature (C), Respiratory Rate (breaths/min)

<Programming Note>

ETC.= for SO: Cohort 4B CD388 - Pooled Placebo

It can be presented separately (i.e., IM one page and SQ another).

Table 14.2.22 Template T5.2: Summary of Potentially Clinically Significant (PCS) Values Vital Signs (Safety Population)

Table 14.3.3.2
Number (Percentage) of Subjects with Potentially Clinically Significant (PCS) Values in Vital Signs at Post-baseline Visit
Safety Population

Parameter / PCS TimepointCriteria	IM Route				SQ Route				ETC. (N = XX)
	CD388 50 mg (N = XX)	CD388 150 mg (N = XX)	CD388 450 mg (N = XX)	Pooled Placebo (N = XX)	CD388 50 mg (N = XX)	CD388 150 mg (N = XX)	CD388 450 mg (N = XX)	CD388 900 mg (N = XX)	
	n/m (%)	n/m (%)	n/m (%)	n/m (%)	n/m (%)	n/m (%)	n/m (%)	n/m (%)	

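### By-visit PCS percentages in shells T4.2 and T5.2 have no assessed-at-that-visit condition in the denominator, so pooled-placebo rates are understated at visits that only some cohorts have

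*SAP*

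**What the plan says.** SAP section 8, Table 6, plans two kinds of PCS summary. One counts subjects with a PCS value at any time after baseline. The other is by visit: for laboratory data, "Number and percentage of subjects with a laboratory value that is deemed PCS, for each scheduled post baseline assessment time point"; for vital signs, "Number and percentage of subjects with a vital sign value that is PCS, for each scheduled postbaseline assessment time point". SAP 8.2 and Protocol 12.3 also plan PCS incidence by time point.

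Templates T4.2 (Table 14.3.2.6, laboratory) and T5.2 (Table 14.3.3.2, vital signs) hold both kinds of row in one table. Each has a single footnote. The numerator is defined by "n is the number of subjects who met the PCS criteria", and the denominator by "Denominator (m) is the number of subjects with non-PCS baseline and at least one post-baseline assessment". The SAP gives no other PCS denominator.

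On columns, SAP section 8 says "summary tables for safety assessments will be presented by injection route (IM or SQ), CD388 dose, and pooled placebo for the safety population". Each CD388 column is therefore one cohort, and each placebo column is a pool of cohorts.

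The schedules differ by cohort:
- Cohorts 1A and 1B have outpatient visits on Days 45, 60, 90 and 120.
- In the first dosing period, Cohorts 2A to 3B have Day 45 and then visits at about 2, 3 and 4 half-lives. OV2 may be omitted.
- Only Cohorts 2A to 3B have second-dose visits, with outpatient days 45, 84, 126 and 168 (Protocol Table 2, footnote a).
- Cohort 4B has Days 45, 84, 126, 168 and 206. Protocol Table 3 marks laboratory tests and vital signs at Day 206, and no other cohort has them then.

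**The concern.** The footnote suits the any-visit rows, where one assessment after baseline is enough to be at risk of being counted. In a visit row it does not require a value at that visit. A placebo subject whose cohort has no such visit can never enter n but stays in m. The CD388 cohort that has the visit is not diluted in this way, because its column contains no other cohort.

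Laboratory tests and vital signs belong to the primary endpoint after the first dose and to a secondary endpoint after the repeat dose. A by-visit table that understates the placebo background rate makes CD388 look worse by comparison, and it does so at late and repeat-dose visits.

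**Working it through.** **Step 1: reproduce the planned numbers (SAP Table 2).** Each cohort has 1 + 7 = 8 CD388 and 1 + 2 = 3 placebo subjects. IM, three cohorts: 24 and 9. SQ, four cohorts: 32 and 12. The total is 24 + 9 + 32 + 12 = 77, as stated. The documents give no by-visit PCS denominator to reproduce.

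**Step 2: formula.** Let a be the placebo subjects whose cohort has the visit, and t all pooled placebo subjects on that route. With full attendance and no PCS value at baseline, the footnote gives n/t and a visit-specific rule gives n/a. The printed rate is a/t of the visit-specific rate, so the cut is 1 − a/t.

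**Step 3: results.**

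| Visit | a | t | Cut | One placebo event: as written v visit-specific |
|---|---|---|---|---|
| SQ, Day 206 (4B only) | 3 | 12 | 3/4 | 1/12 = 8.3% v 1/3 = 33.3% |
| SQ, visit shared by three of four cohorts | 9 | 12 | 1/4 | 1/12 = 8.3% v 1/9 = 11.1% |
| SQ, second dose (2B, 3B) | 6 | 12 | 1/2 | 1/12 = 8.3% v 1/6 = 16.7% |
| IM, second dose (2A, 3A) | 6 | 9 | 1/3 | 1/9 = 11.1% v 1/6 = 16.7% |
| SQ, day that only 1B has | 3 | 12 | 3/4 | 1/12 = 8.3% v 1/3 = 33.3% |
| IM, day that only 1A has | 3 | 9 | 2/3 | 1/9 = 11.1% v 1/3 = 33.3% |
| First-dose inpatient days | 9 or 12 | 9 or 12 | 0 | no difference |

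**Step 4: what the first-dose outpatient rows depend on.** The SAP does not say whether visits are keyed by day or by OV label.
- By OV label, 1B, 2B and 3B share OV2 to OV4 (9 of 12). The three IM cohorts share all of them (9 of 9), so IM has no cut.
- By day, Days 60, 90 and 120 may belong to 1A or 1B alone. Cohorts 2B and 3B would join 4B on Days 84, 126 and 168 if their half-life-based visits fall there. That assumes a half-life of 42 days, as the second-dose schedule implies (84/2 = 126/3 = 168/4 = 42).

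**Step 5: second-dose rows.** SAP 10.3 takes the predose value on the second dosing date as baseline for second-dose analyses. If m is rebuilt from it, subjects in 1A, 1B and 4B have no such baseline and drop out. Placebo becomes 6 of 6 on each route and the cut is zero. If m is not rebuilt, the cuts in the table apply, and the 50 mg and 900 mg columns would show 0/8 at visits those cohorts never have.

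**Step 6: sensitivity to PCS baselines.** Suppose 0 to 2 attending and 0 to 2 non-attending placebo subjects are excluded for a PCS baseline. The cut then ranges over 0.70–0.90 (3/12), 0.10–0.30 (9/12), 0.40–0.60 (6/12), 0.14–0.43 (6/9) and 0.57–0.86 (3/9).

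**Step 7: illustration.** The expected printed placebo rate is the true rate times a/t. At Day 206, assumed true rates of 5%, 10% and 20% in both arms would print in expectation as 1.25%, 2.5% and 5% for placebo. The 900 mg column (8 of 8) would keep the true rate.

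**The case against.** The best defence is that shells are not final tables. Their preamble allows layout and footnotes to change. T4.2 prints n/m in each cell, so a programmer could vary m by row. The only labelled visit block drawn in either PCS shell is a predose one, which looks like a placeholder. This shows that a sensible programmer might avoid the error. It does not remove the written rule, which contains no visit condition. T5.2 is weaker still: its header says n/m, but its cells show only a count and a percentage, so a reader would not see m.

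The second defence is SAP 10.3, and it largely stands: built on the second-dose baseline, the second-dose cuts and the 0/8 cells disappear. But the PCS shells do not say so. They also lack the second-dose versions, limited to Cohorts 2A to 3B and their placebo, that the TEAE shells have.

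Third, Day 206 can be questioned. The first part of SAP Appendix C stops at Day 168, and the final adverse-event contact for 4B is described as a telephone call. The Appendix C gap may be a text-extraction artefact. Protocol Table 3 does mark laboratory tests and vital signs at that visit, and PK samples are also scheduled then. With three placebo subjects the corrected percentage moves in steps of 33 points and says little by itself.

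Fourth, the practical effect is limited. T4.1 shows n by visit, the listings carry PCS flags, escalation rests on blinded review of safety data, and there is no hypothesis test. All of this stands and lowers the stakes.

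A reader might infer that the tables will show a false safety signal for CD388 at every late or repeat-dose visit. The documents do not support that. The bias is an expectation, and in groups of 8 and 3 to 6 many cells will have no events. CD388 dropouts also stay in m under the literal rule, which lowers CD388 percentages too.

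**Conclusion.** The concern holds for the rule as written. T4.2 and T5.2 apply one denominator to two kinds of row, and it is wrong for the by-visit rows. The schedule mismatch understates pooled placebo by one quarter to three quarters at visits that only some cohorts have, and it biases the comparison against CD388 in expectation.

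The firmest case is Day 206, at three quarters, because it does not depend on the second-dose baseline. The one-third (IM) and one-half (SQ) cuts at second-dose visits are conditional: they apply only if m is not rebuilt from SAP 10.3. A reader who looks only at the second dose might take one third as the smallest cut, but an SQ visit shared by three of four cohorts gives one quarter. First-dose outpatient cuts depend on the visit key.

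These sizes assume planned numbers, full attendance and no PCS value at baseline. First-dose inpatient days, which all cohorts share, are not affected by the mismatch. No test or sample size is touched. What suffers is the by-visit display of a primary and a secondary safety endpoint.

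**What to change.** - Keep the present m for the any-visit rows of T4.2 and T5.2.
- For each visit row, define m as subjects whose baseline for that dose period is not PCS and who have a non-missing value of that parameter at that visit.
- Present second-dose PCS results separately for Cohorts 2A, 2B, 3A and 3B and their placebo subjects, as the TEAE shells already do.
- State whether visits are keyed by study day or by OV label.
- Print NA in columns whose cohort does not have the visit.

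The cost is a revised footnote, second-dose versions of two shells and minor programming. No new data are needed. The downside is that some placebo denominators become visibly small, from 3 to 6, which is the actual amount of information at those visits.
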